8. IMMUNE CELL CHARACTERIZATION

Humoral (immunoglobulin; antibody) immune assays will be performed at Screening, at the 300 mg Up-dosing Visit, and at the Exit or Early Discontinuation Visit. The blood samples for these serum-based assays can and should be collected with the same blood draw as the CBC.

8.1 Peanut-Specific Antibody (Immunoglobulin) Assays

Antigen immunotherapy has been shown to induce antigen-specific humoral responses. The balance of isotypic response may play a role in allergen sensitivity (eg, an increase of IgG/IgE).

The blood sample for antibody analysis should be collected with the same blood draw as the CBC. Collection of a sample for antibody analysis, like the CBC, is mandatory.

At each of the specified time points, a sample of serum will be stored for assessment of peanut- and peanut component-specific antibody levels (immunoglobulin assays). Total IgE and specific IgE and IgG4 will be measured using UniCAP. Peanut-specific IgE and IgG4 (included in the immunoglobulin assays) will be measured at the Screening, 300 mg Up-dosing, Exit, and Early Discontinuation Visits. Additionally, as part of the Screening/Baseline immunoglobulin assays, component-resolved (peanut component proteins) peanut IgE testing will be performed. The amount of blood to be drawn will be determined on the basis of the requirements of the test and individual laboratory protocols, in compliance with local regulations.

9. STATISTICAL CONSIDERATIONS

This section outlines the major statistical consideration for Study ARC010. A comprehensive statistical analysis plan (SAP) will be finalized prior to overall study unblinding.

Data will be summarized descriptively by treatment arm and overall. The descriptive summary for the categorical variables will include counts and percentages. The descriptive summary for the continuous variables will include means, medians, standard deviations, and minimum and maximum values.

All data will be listed for all subjects.

9.1 Analysis Populations

The ITT population (ie, the Full Analysis Set) will consist of all randomized subjects who received at least 1 dose of randomized study treatment (AR101 or placebo). Subjects will be analyzed according to randomized treatment. The ITT population will be used as the primary analysis population for all analyses of efficacy endpoints.

Since only a small number of subjects are expected to be randomized but not treated and due to the double-blind nature of the trial, no bias is introduced by excluding these subjects from the ITT population. In order to verify this expectation, sensitivity analyses will be performed using the randomized population for the primary and key secondary endpoints.

The Completer population will include all subjects in the ITT population who undergo the Exit DBPCFC.

A Per Protocol (PP) population may be defined for this study. The PP population will be a subset of the Completer population, limited to subjects who have no major protocol deviations that may influence the desensitization response. Exclusions will be determined by blinded review before database lock and overall study unblinding. Subjects will be analyzed according to randomized treatment.

Sensitivity analyses, to be described in full in the SAP, will be performed using the Completer population and PP population (the latter if sufficiently different from the Completer population).

The Safety population will consist of all subjects who receive randomized study treatment. The Safety population will be used for summaries of safety parameters. Subjects will be analyzed according to treatment received.

9.2 Study Endpoint Assessment

9.2.1 Primary Endpoint

The primary endpoint is the proportion of subjects who achieve desensitization as determined by tolerating 1000 mg as a single dose (2043 mg cumulative) of peanut protein (ie, a top single challenge dose of 1000 mg) with no more than mild symptoms at the Exit DBPCFC (ie, responders).

An ITT analysis will be performed as the primary efficacy analysis to test for a treatment difference in the response rate. All individuals failing to achieve the success definition described above will be considered treatment failures, as will subjects who fail to achieve and maintain a 300 mg daily dose of IP (escalation failure non-responders). All individuals

who drop out of the study or discontinue OIT prior to undergoing the Exit DBPCFC will be considered treatment failures (ie, Missing = Failure).

Fisher's exact test will be used to test the treatment difference for desensitization and exact CIs will be constructed as follows: (1) exact Clopper Pearson confidence limits will be used for the binomial proportion and (2) exact unconditional confidence limits based on the score statistic will be used for the difference in proportions.

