1.2.1 ARC001 Trial

ARC001 was a multicentre, randomized, double-blind, placebo-controlled study of the efficacy and safety of AR101 (characterized peanut allergen) OIT in peanut-allergic children and adults (4 to 26 years of age). The study consisted of a Screening Period, including a Screening DBPCFC, an initial escalation period, an Up-dosing Period, and a Maintenance Period, followed by an Exit DBPCFC.

All eligible subjects underwent a DBPCFC of up to 100 mg (143 mg cumulative) of peanut protein or placebo during the Screening portion of the study. Those subjects who had dose-limiting symptoms (DLS) at or before the 100 mg (143 mg cumulative) challenge dose of peanut protein (measured as 200 mg of peanut flour) were randomized 1:1 to AR101 or placebo.

Subjects received daily oral dosing of AR101 or placebo OIT; all escalation doses occurred in a clinical research center (CRC) or other monitored setting and were administered under direct observation.

After the subjects had been up-dosed to a 300 mg/d dose and had continued to receive that dose for 2 weeks, subjects underwent a DBPCFC of up to 600 mg (1043 mg cumulative) of peanut protein or placebo.

All placebo subjects who completed ARC001 were eligible for rollover into the ARC002 trial. Placebo subjects in ARC002 underwent an escalation and up-dosing schedule identical to that for AR101 subjects in the ARC001 protocol. All subjects on AR101 who passed the DBPCFC by tolerating ≥ 443 mg cumulative of peanut protein with no more than mild symptoms were eligible to proceed to ARC002. Those who did not pass were considered treatment failures.

Efficacy Results:

Fifty-six subjects were randomized: 29 subjects to AR101 and 27 subjects to placebo. Consent for 1 subject was withdrawn after the subject was randomized but before the first dose of study treatment was administered. The intent-to-treat (ITT) population comprised 55 subjects in total, 29 in the AR101 and 26 in the placebo arm. The 2 study groups were overall well matched for baseline characteristics including baseline sensitivity in the Screening DBPCFC. Six subjects in the AR101 arm withdrew from the study prior to the Exit DBPCFC.

For the primary efficacy analysis conducted in the ITT population, AR101 was statistically significantly superior to placebo, with 23 of 29 (79%) AR101 desensitization responders as compared to 5 of 26 (19%) placebo desensitization responders ($p < 0.0001$ by Fisher's exact test).

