9.2.2.1 Analysis of Key Secondary Endpoints

- The proportion of subjects who tolerate at least 600 mg as a single dose (1043 mg cumulative) of peanut protein with no more than mild symptoms at the Exit DBPCFC: The statistical analysis to be conducted for this key secondary endpoint will be similar to that used as for the primary endpoint.
- The proportion of subjects who tolerate at least 300 mg as a single dose (443 mg cumulative) of peanut protein with no more than mild symptoms at the Exit DBPCFC: The statistical analysis to be conducted for this key secondary endpoint will be similar to that used as for the primary endpoint.
- The maximum severity of symptoms occurring following ingestion of peanut protein during the Exit DBPCFC: The objective of analyzing this key secondary efficacy endpoint is to show that subjects from the AR101 group will have less chance of developing more severe levels of symptom severity compared to subjects from the placebo group. Symptom severity will be recorded at 4 levels: 0-None, 1-Mild, 2-Moderate, 3-Severe. Symptom severity data will be collected at each challenge dose of peanut protein during the Exit DBPCFC – 3 mg, 10 mg, 30 mg, 100 mg, 300 mg, 600 mg, and 1000 mg; the maximum severity will be used for each subject in the analysis.

The maximum symptom severity observed at any challenge dose in the Exit DBPCFC will be used for each subject in the primary analysis of this key secondary endpoint. Subjects without an Exit DBPCFC will have their maximum severity during the Screening DBPCFC used, which equates to no change from Screening.

The number and percent of subjects by maximum severity at the Exit DBPCFC will be tabulated by treatment arm. The Cochran-Mantel-Haenszel statistic (with equally spaced scores) will be used to test for a treatment difference. The mean of the numerical values assigned to maximum severity by treatment group will also be reported.

As supportive analyses, the analysis of maximum severity of symptoms during the Exit DBPCFC will be repeated for the maximum severity observed in the DBPCFC at

any dose up to a maximum challenge of 600 mg. The analysis will be repeated up through a maximum challenge of 300 mg, 100 mg, 30 mg, 10 mg, and 3 mg.

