The key secondary efficacy endpoints will be tested in the ITT population in the hierarchical order specified above. Each comparison will be evaluated for statistical significance (two-sided $p < 0.05$) only if all of the preceding tests (not including supportive tests) in the hierarchy and the primary analysis of the primary endpoint are statistically significant in favor of AR101. The ITT population will be used as the primary population for analysis of key secondary endpoints. This closed testing procedure maintains the overall Type I error rate at 0.05 ([EMEA CPMP, 2002](#); [Cook et al, 2008](#)). If any of the preceding tests are not significant, the p-value will be displayed for informational purposes only.

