9.4 Sample Size and Power Calculations

The sample size for the study, approximately 160 subjects randomized 3:1 (AR101:placebo), has sufficient power to detect a treatment effect for the primary efficacy analysis. In Study ARC001, the placebo group response rate (95% CI) in the ITT population was 19% (7%, 39%) and 0% (0%, 13%) at 443 mg and 1043 mg cumulative peanut, respectively. Subjects were enrolled in Study ARC001 if at the Screening DBPCFC they expressed DLS at ≤ 144 mg cumulative peanut protein whereas in Study ARC010 they will be enrolled if they express DLS ≤ 443 mg cumulative peanut protein. Extrapolating to Study ARC010, where the primary efficacy endpoint is response rate in the ITT population at 2043 mg cumulative peanut protein, the placebo response rate is assumed to be at most 15%. With these considerations, a sample size of 120 AR101 and 40 placebo subjects and a 15% placebo response rate, there is at least 80% power to detect a response rate of 39% or higher in the

AR101 group using Fishers exact test with a 0.05 two-sided Type I error rate. Under the same assumptions, there is at least 90% power to detect a response rate of at least 43% in the AR101 group.

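### Does leaving the inversion of the exact unconditional score limits unstated make the primary result unreliable or open to later choice?

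*Protocol*

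**What the plan says.** For the primary endpoint, Section 9.2.1 states that Fisher's "exact test will be used to test the treatment difference for desensitization". It then names two kinds of interval: Clopper-Pearson limits for each proportion and, for the treatment contrast, "exact unconditional confidence limits based on the score statistic will be used for the difference in proportions". It gives no confidence level for the latter and does not name the inversion.

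Section 9.2.2.1 extends the approach to the 600 mg and 300 mg responder endpoints: "The statistical analysis to be conducted for this key secondary endpoint will be similar to that used as for the primary endpoint". In the testing hierarchy, "Each comparison will be evaluated for statistical significance" at a two-sided p below 0.05, and only if the primary analysis and all earlier tests are significant in favour of AR101. No section uses the interval for the difference to decide success.

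Section 9.4 powers the trial on the same test, the "AR101 group using Fishers exact test with a 0.05 two-sided Type I error rate". The opening of Section 9 describes itself as an outline and refers to a comprehensive SAP to be finalized before overall unblinding.

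**The concern.** Fisher's test is conditional on the margins and the interval is unconditional, so the two need not agree about zero. The words of Section 9.2.1 fit two different intervals:

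- **A:** invert two one-sided 2.5% score tests.
- **B:** invert one two-sided 5% score test.

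For some tables A includes zero and B excludes it, although Fisher's p is below 0.05 in both cases. If the choice were still open at unblinding, a software option could decide whether a significant primary result appears beside an interval that includes no difference. The apparent contrast is stark: judged only by the test at zero difference, the mismatch at the minimum detectable effect is 11% under A and 0% under B.

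**Working it through.** **Inputs.** Section 9.4: 120 AR101 and 40 placebo subjects, placebo rate 15% (the assumed maximum), AR101 rates of 39% and 43%, two-sided 0.05. A 95% interval is assumed, since Section 9.2.1 states no level.

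**Step 1: the plan's own figures.** Power is the sum of Bin(x₁;120,p₁)·Bin(x₂;40,p₂) over all tables (121 × 41) that favour AR101 with Fisher p < 0.05.

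| AR101 vs placebo | Probability-ordered Fisher | Fisher at 0.025 per tail | Protocol |
|---|---|---|---|
| 39% vs 15% | 82.8% | 80.4% | at least 80% |
| 43% vs 15% | 92.1% | 90.8% | at least 90% |

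The stated power reproduces and does not involve the interval.

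**Step 2: the interval.** For a difference d,

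Z(d) = (p̂₁ − p̂₂ − d) / √[p̃₁(1−p̃₁)/120 + p̃₂(1−p̃₂)/40],

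with p̃ the maximum likelihood estimates restricted to p̃₁ − p̃₂ = d. The unconditional p-value is the largest tail probability of Z(d) over the nuisance rate. At d = 0, zero is excluded under A when z is at least 2.345, and under B when |z| is at least 1.963.

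**Step 3: an example where A and B differ.** For 41/120 vs 6/40:

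- Difference: 0.3417 − 0.1500 = 0.1917.
- Pooled rate: 47/160 = 0.29375.
- Standard error: √[0.29375 × 0.70625 × (1/120 + 1/40)] = 0.0832.
- z = 0.1917/0.0832 = 2.305.

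Fisher p is 0.027. The unconditional p is 0.0293, which is above 0.025, so A includes zero. It is below 0.05, so B excludes zero.

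**Step 4: how often A disagrees, judged at d = 0 (probability-ordered Fisher).**

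| True rates | Fisher p < 0.05 and A includes 0 |
|---|---|
| 39% vs 15% | 11.3% |
| 43% vs 15% | 6.7% |
| 50% vs 15% | 1.8% |
| 62% vs 15% | 0.03% |
| 39% vs 10% | 4.4% |
| 39% vs 5% | 0.4% |

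Scanning negative differences as well gives 11.6% to 12.0% at 39% vs 15%, depending on the grid.

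**Step 5: B is not free of the problem.** A reported interval runs from the smallest to the largest difference not rejected. The two-sided p-value does not fall steadily as d moves below zero. For 38/120 vs 6/40:

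- Pooled rate 44/160 = 0.275 and z = 0.1667/0.0815 = 2.044. Fisher p is 0.043.
- At d = 0 the two-sided p is 0.042, so zero is rejected.
- At d = −0.01 it is 0.067, so −0.01 is not rejected.

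The lower limit is therefore below zero. Over all tables, B's interval includes zero beside a significant Fisher test as follows; the lower figure is from a coarser scan.

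| True rates | Fisher p < 0.05 and B includes 0 |
|---|---|
| 39% vs 15% | 4.0% to 5.3% |
| 43% vs 15% | 2.3% to 3.1% |
| 50% vs 15% | 0.7% to 0.8% |

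Judged only at d = 0, B gives 0% here, but then excludes zero with Fisher p ≥ 0.05 in 1.5% of trials at 39% vs 15%. That reverse mismatch disappears when the interval spans all differences not rejected, so the 1.5% and the 4% to 5% belong to two readings of B and do not add.

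**Step 6: other settings matter too.** With Fisher at 0.025 per tail, A's 11.3% becomes 8.8%. Restricting the nuisance range (Berger-Boos, 0.0001) brings it to about 0%. Inversion is one of several computational options and not clearly the decisive one.

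**The case for a change.** The strongest case is that the protocol is not silent here: it fixes a conditional test beside an unconditional interval, and no sentence says which prevails if they disagree. The disagreement is most frequent near the effects for which power is claimed. For 47/120 vs 8/40 (Fisher p = 0.034) A runs from −0.002 to 0.332 and B from 0.007 to 0.328, so the same data can be shown with or without zero in the interval.

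Those facts stand, but they do not make an error. Precedence is settled in substance, because Section 9.2.2.1 makes the p-value the criterion. Fear of a choice after unblinding presumes that the SAP is silent, while Section 9 commits to finalizing it before overall unblinding. The SAP was not available for this review, and its content cannot be held against the protocol.

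Nor is B plainly better. It still leaves a mismatch, and it gives up the guarantee of 2.5% in each tail: at zero difference one tail can reach 3.6%. A keeps that guarantee at the price of wider limits. Reasonable statisticians choose either.

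**Conclusion.** The concern does not hold. Section 9.2.1 names the test, the class of interval and the statistic. What it leaves open is a computational setting that a SAP ordinarily supplies, and either setting gives a valid interval. The success decision, type I error and stated power do not depend on it.

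What remains is a possible oddity of reporting. At 39% vs 15%, a significant p-value sits beside an interval including zero in 11% to 12% of trials with two one-sided tests, and in 4% to 5% with one two-sided test. The apparent 0% against 11% compares tests at zero difference, not the intervals that would be reported. The sizes assume a 95% level, 120 and 40 subjects, the probability-ordered Fisher p-value and no restriction of the nuisance range. They are largest at the minimum detectable effect with placebo response at its assumed ceiling. At the ARC001 rates for the 300 mg dose ("with 23 of 29 (79%) AR101 desensitization responders as compared to 5 of 26 (19%) placebo desensitization responders") the mismatch under two one-sided tests is below 0.0001%. At most, a reader with the SAP may confirm that it names the level and the inversion.

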9.2.2 Secondary Endpoints

The secondary endpoints are defined in [Section 3.8](#), and a full description of the analyses planned for each will be provided in the SAP. A brief description of the planned analyses for the key secondary efficacy endpoints and other selected secondary endpoints is provided below.

9.2.2.1 Analysis of Key Secondary Endpoints

- The proportion of subjects who tolerate at least 600 mg as a single dose (1043 mg cumulative) of peanut protein with no more than mild symptoms at the Exit DBPCFC: The statistical analysis to be conducted for this key secondary endpoint will be similar to that used as for the primary endpoint.
- The proportion of subjects who tolerate at least 300 mg as a single dose (443 mg cumulative) of peanut protein with no more than mild symptoms at the Exit DBPCFC: The statistical analysis to be conducted for this key secondary endpoint will be similar to that used as for the primary endpoint.
- The maximum severity of symptoms occurring following ingestion of peanut protein during the Exit DBPCFC: The objective of analyzing this key secondary efficacy endpoint is to show that subjects from the AR101 group will have less chance of developing more severe levels of symptom severity compared to subjects from the placebo group. Symptom severity will be recorded at 4 levels: 0-None, 1-Mild, 2-Moderate, 3-Severe. Symptom severity data will be collected at each challenge dose of peanut protein during the Exit DBPCFC – 3 mg, 10 mg, 30 mg, 100 mg, 300 mg, 600 mg, and 1000 mg; the maximum severity will be used for each subject in the analysis.

The maximum symptom severity observed at any challenge dose in the Exit DBPCFC will be used for each subject in the primary analysis of this key secondary endpoint. Subjects without an Exit DBPCFC will have their maximum severity during the Screening DBPCFC used, which equates to no change from Screening.

The number and percent of subjects by maximum severity at the Exit DBPCFC will be tabulated by treatment arm. The Cochran-Mantel-Haenszel statistic (with equally spaced scores) will be used to test for a treatment difference. The mean of the numerical values assigned to maximum severity by treatment group will also be reported.

As supportive analyses, the analysis of maximum severity of symptoms during the Exit DBPCFC will be repeated for the maximum severity observed in the DBPCFC at

any dose up to a maximum challenge of 600 mg. The analysis will be repeated up through a maximum challenge of 300 mg, 100 mg, 30 mg, 10 mg, and 3 mg.

The key secondary efficacy endpoints will be tested in the ITT population in the hierarchical order specified above. Each comparison will be evaluated for statistical significance (two-sided $p < 0.05$) only if all of the preceding tests (not including supportive tests) in the hierarchy and the primary analysis of the primary endpoint are statistically significant in favor of AR101. The ITT population will be used as the primary population for analysis of key secondary endpoints. This closed testing procedure maintains the overall Type I error rate at 0.05 ([EMEA CPMP, 2002](#); [Cook et al, 2008](#)). If any of the preceding tests are not significant, the p-value will be displayed for informational purposes only.

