4. SELECTION AND WITHDRAWAL OF SUBJECTS

4.1 Inclusion Criteria

Subjects who meet all of the following criteria are eligible for enrollment as study subjects:

1. Age 4 through 17 years (inclusive)
2. Clinical history of allergy to peanuts or peanut-containing foods

3. Serum IgE to peanut of ≥ 0.35 kUA/L (as determined by UniCAP™ within the past 12 months) and/or a peanut SPT wheal diameter ≥ 3 mm compared to control
4. Experience DLS at or before the 300 mg (444 mg cumulative) challenge dose of peanut protein (measured as 600 mg of peanut flour) on Screening DBPCFC conducted in accordance with PRACTALL guidelines
5. Written informed consent from subjects or parent/guardian for all subjects (or both parents when required by local authorities)
6. Written assent from minor subjects as appropriate (in accordance with local regulatory requirements)
7. Use of effective birth control by female subjects of childbearing potential ([Section 7.10.3.2](#))

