- Serum pregnancy test for females of childbearing potential (pregnancy test result must be available prior to the DBPCFC)
- Blood draw (same venipuncture for all samples), at any time during Screening prior to the DBPCFC, to collect samples for:
 - Peanut- and peanut component-specific IgE, total IgE, and peanut-specific IgG4 assays
 - Complete blood cell count (CBC)
 - Optional blood sample for immune cell characterization assays

The amount of blood to be taken in total for all tests (required immunoglobulin and CBC and optional immune cell characterization assays) will be included in the manual of procedures and not exceed a total volume of 2.5 mL/kg, to a maximum total of 70 mL on any study day. Blood draw should be collected in compliance with local laboratory guidelines and testing regulations. Multiple attempts to obtain blood, and repeat samples can be collected where necessary for damaged samples or safety reasons.

- SPT to peanut extract
- Confirmation subject or subject's parent or guardian has an unexpired epinephrine auto-injector prior to leaving the clinic following Day 1 of the DBPCFC

- DBPCFC conducted in accordance with PRACTALL guidelines, with assessments made by a Blinded Evaluating Physician (Blinded Assessor), as described in [Section 6.6](#).
- Monitoring for AEs, including allergic symptoms ([Section 6.7](#)) commences from the time the consent/assent form is signed
- Subjects will be instructed to continue to follow a peanut-avoidant diet for the duration of the study.
- Subjects and parents or guardians will additionally receive teaching about food/peanut allergy according to the investigational site's established standards. This is to include at a minimum the following topics (some or all of which may be addressed in a comprehensive anaphylaxis action plan):
 - Recognition of an allergic reaction and of the symptoms of anaphylaxis
 - When and how to administer epinephrine via auto-injector
 - Requirement to go to nearest emergency facility following use of epinephrine auto-injector
 - Ways to minimize the risk of accidental exposure to peanut in, and outside of, the home (may be supplemented by referral to recognized food allergy organizations for access to additional learning materials)

The laboratory values and clinical findings, including those from the Screening DBPCFC, will serve as the baseline measures for comparison to subsequent measures obtained during the course of the study.

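### The test of maximum Exit symptom severity names no stratification by Screening severity and may give up a little power

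*Protocol*

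**What the plan says.** Protocol section 9.2.2.1 defines the outcome on an ordinal scale: "Symptom severity will be recorded at 4 levels: 0-None, 1-Mild, 2-Moderate, 3-Severe". Each subject contributes the worst grade seen at any Exit challenge dose. The test is given in one sentence: "The Cochran-Mantel-Haenszel statistic (with equally spaced scores) will be used to test for a treatment difference". The score system is fixed, but no stratum or covariate is mentioned.

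Missing Exit challenges are handled in the same section: "Subjects without an Exit DBPCFC will have their maximum severity during the Screening DBPCFC used, which equates to no change from Screening". Section 6.2 gives the Screening results their role: "clinical findings, including those from the Screening DBPCFC, will serve as the baseline measures".

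The next section, 9.2.2.2, includes baseline maximum tolerated dose in both tolerated-dose models. Severity is thus the only graded Exit challenge outcome described without a baseline term. Section 9.2.2 calls these descriptions brief and leaves the full account to the SAP, which was not available for this check.

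**The concern.** A pre-randomisation measurement of the outcome is available and goes unused in the comparison. If Screening severity predicts Exit severity, comparing arms within Screening grades removes variance that the pooled comparison keeps.

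The carry-forward rule strengthens the case. For a subject with no Exit challenge, the outcome is the Screening grade, so some baseline-outcome correlation is built in. With 21% dropout it is about 0.16 in the AR101 arm even when the two challenges are otherwise unrelated.

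The endpoint also occupies a gate. It is the last key secondary, and section 9.2.2.2 allows formal testing of the other secondary endpoints only if all key secondaries succeed.

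**Working it through.** **1. The plan's own power figure.** Section 9.4 uses "a sample size of 120 AR101 and 40 placebo subjects and a 15% placebo response rate" and "Fishers exact test with a 0.05 two-sided Type I error rate". Exact power is the sum, over all pairs (a, c), of Bin(a; 120, p) × Bin(c; 40, 0.15) for tables where Fisher's p < 0.05. This gives 82.8% at p = 0.39 and 92.1% at p = 0.43. Both of the protocol's statements (at least 80%, at least 90%) hold. No power is stated for severity.

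**2. The two statistics.** In stratum h, let T be the sum of AR101 scores, E = n1 × the stratum mean score, and V = n1 × n2 × s² / n, where s² is the stratum variance of the scores. Then Q = [Σ(T − E)]² / ΣV, on 1 degree of freedom. The unstratified test has one stratum. The stratified test has one per Screening grade.

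**3. Assumptions, because the documents give no figures.**
- Latent-normal severity at both challenges.
- Screening mild/moderate/severe split 35/55/10% or 15/70/15%.
- Placebo Exit none/mild/moderate/severe 3/12/60/25%.
- Latent correlation 0, 0.3 or 0.5.
- AR101 dropout 0 or 21% (6/29 in ARC001, section 1.2.1), none on placebo, with Screening severity carried forward.

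**4. The planned effect on this scale.** Taking none or mild as the responder cut:
- No dropout: Φ⁻¹(0.39) − Φ⁻¹(0.15) = −0.279 + 1.036 = 0.757.
- 21% AR101 dropout counted as failure: completers need 0.39/0.79 = 49.4%, a shift of about 1.02.

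**5. Power at 39% v 15%, unstratified → stratified (%).**

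| Screening split | AR101 dropout | corr. 0 | corr. 0.3 | corr. 0.5 |
|---|---|---|---|---|
| 35/55/10 | 0 | 95.7 → 95.6 | 95.6 → 96.3 | 95.5 → 97.6 |
| 35/55/10 | 21% | 99.5 → 99.4 | 99.5 → 99.7 | 99.5 → 99.9 |
| 15/70/15 | 0 | 95.5 → 95.3 | 95.8 → 96.6 | 95.7 → 97.8 |
| 15/70/15 | 21% | 98.3 → 98.2 | 98.5 → 99.0 | 98.4 → 99.5 |

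The gain here is 0 to about 2 points. Requiring a significant primary test as well changes joint power by 0.1 point or less (for example 82.4% → 82.5%). At 62%, the ARC001 AR101 rate at 600 mg, both tests have 100% power.

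**6. Less favourable outcome distributions.** Step 5 implies that no placebo non-responder stops on mild symptoms, although section 6.6 allows mild symptoms to be dose limiting.
- *Non-responders given the Screening split; 80% of responders mild, 20% none.* Unstratified power falls to 41–57% at 39% v 15% and 52–70% at 43% v 15%. With 21% dropout, stratifying adds about 1–3 points at correlation 0.3 and 3–4 at 0.5. With no dropout it adds about 0–2. At correlation 0 the tests agree within 1 point. The gain survives the primary gate (for example 53.1% → 57.2%); the 600 mg and 300 mg gates were not simulated.
- *40% of placebo none or mild, 21% AR101 dropout, shift 0.76.* Unstratified power is 66–79% and the gain 4–9 points. If 15% still marks the placebo responder cut, this shift gives 0.39 × 0.79 = 31% AR101 responders, below the planned 39%.

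Across further assumed splits, before the earlier gates, the gain was about 0–5 points near the design effect at correlation 0.3–0.5, and about 2–11 points at weaker effects.

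**7. Does stratifying mend the carry-forward?** With 21% v 0% dropout and no effect among completers, rejection was about 5–7% unstratified and 6–9% stratified. It does not.

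**The case against.** The strongest reply is that nothing here is wrong. The unstratified test is valid, and its null distribution already allows for chance imbalance in Screening severity. The protocol is silent on strata rather than excluding them, the named method accepts them, and the full description is deferred to the SAP. All of that stands. What remains is that section 9.2.2.1 fixes the statistic, the scores and the imputation, while 9.2.2.2 names its baseline terms, so a reader would take the severity test as unstratified.

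The correlation also has no source. Every randomised subject had to meet "Experience DLS at or before the 300 mg (444 mg cumulative) challenge dose of peanut protein" at Screening, which narrows the range of Screening grades and may limit their prognostic value. That is why the gain can only be given as a range starting at zero.

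Three stronger readings are tempting and are not supported:
- *A loss of 7 to 10 points.* At correlation 0.5, a 35/50/15% Screening split and 21% AR101 dropout, power does rise from 76% to 86% (shift 0.7) and from 87% to 94% (shift 0.8). But shift 0.7 means Φ(−1.036 + 0.7) = 36.8% of completers, and 36.8% × 0.79 = 29% overall. Shift 0.8 gives 40.7% × 0.79 = 32%. Primary power there is only 40% and 55%, so the severity test would often not be reached. These effects are below the planned one.
- *That the gate is in serious danger.* Severity is tested only after the primary, 600 mg and 300 mg tests succeed, and those gates absorb part of any benefit. In the step 5 runs, unstratified power given a significant primary was already above 99%.
- *That stratifying repairs the carry-forward.* Step 7 shows slightly more null rejection under unequal dropout, not less.

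**Conclusion.** The point holds as a minor efficiency suggestion, not as an error. Section 9.2.2.1 names no stratification by a baseline that is collected, is designated as baseline, and serves as the outcome for subjects without an Exit challenge. The likely cost is roughly 0–5 points of power near the planned effect if the Screening-Exit correlation is 0.3–0.5. It is more at weaker effects or if many placebo subjects have only mild Exit symptoms, and essentially nothing at correlation 0.

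These sizes rest on an assumed correlation, assumed Screening and placebo Exit distributions and the ARC001 dropout rate, and confidence in them is low. If the SAP already stratifies this test, the point falls away.

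**What to change.** Before unblinding, state in section 9.2.2.1 or the SAP that maximum Exit severity is tested with the Cochran-Mantel-Haenszel row mean score statistic, using the same equally spaced scores and stratified by maximum severity at the Screening challenge (mild, moderate, severe). Keep the unstratified test as supportive.

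The cost is one clause and no new data. A sparse stratum adds little information but does not invalidate the statistic. The change should be described as an efficiency measure only. Any distortion from carrying Screening severity forward under unequal dropout needs its own sensitivity analysis.
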